10.5.4. Pharmacokinetic

PK Parameters

- If one or more non-quantifiable (NQ) values occur in a profile before the first measurable
 concentration, they will be assigned a value of zero concentration. For linear plots, zero
 concentration value(s) before the first measurable concentration will be included in the plot. For
 log-linear plots, zero concentration value(s) before the first measurable concentration will be
 assigned a missing value.
- If a single NQ value occurs between measurable concentrations in a profile, the NQ should generally be set to missing in the derivation of pharmacokinetic parameters, statistical analysis, and the individual subject plots.
- If two or more NQ values occur in succession between measurable concentrations, the profile
 will be deemed to have terminated at the last measurable concentration prior to these NQs. For
 the purpose of individual subject plots, these NQs will be set to 0, and the subsequent
 measurable concentrations will be retained. For the derivation of pharmacokinetic parameters,
 these NQs and any subsequent measurable concentrations will be set to missing.
- NQs which occur after the last measurable concentration will be omitted (set to missing) in the
 derivation of pharmacokinetic parameters and from the individual subject plots.
- Individual's PK parameters reported as 'NC' (Not Calculable) or 'ND' (Not Determined) will be
 included in listings but omitted (set to missing) from figures, summaries and statistical analyses.

10.6. Appendix 6: Premature Withdrawals & Handling of Missing Data

10.6.1. Premature Withdrawals

Element	Reporting Detail
General	Subject study completion was defined as a participant has completed all phases of the study including the last visit or the last scheduled procedure (Follow-up) as described in the protocol.
	Withdrawn subjects maybe replaced in the study.
	All available data from subjects who were withdrawn from the study will be listed and all available planned data will be included in summary tables and figures, unless otherwise specified.

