5.2. Number of Participants

Sufficient Japanese and Caucasian healthy male subjects will be enrolled such 6 subjects of each population complete dosing and critical assessments.

If participants prematurely discontinue the study, additional replacement participants may be recruited and assigned to the same treatment at the discretion of the Sponsor in consultation with the investigator.

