1. REPORTING & ANALYSIS PLAN SYNPOSIS

Overview	Key Elements of the RAP	
Purpose	The purpose of this RAP is to describe the planned analyses and output to be included in the Clinical Study Report for Protocol 204678.	
Protocol	• This RAP is based on the original protocol Dated:19/JUL/2017 of study204678 (GSK Document Number.: 2017N318316_00).	
Primary Objective	• To investigate PK following a single oral dose of Pyrimethamine 50 mg in fasted healthy Japanese male subjects.	
Primary Endpoint	• Cmax, AUC(0-t), AUC(0-inf), AUC(0-24), tmax, t1/2, CL/F, Vd/F from the plasma concentrations of Pyrimethamine in healthy Japanese male subjects, as data permit.	
Study Design	This study will be a single centre, open-label, parallel-group, single oral dose study to evaluate the pharmacokinetic (PK), safety and tolerability of Pyrimethamine in healthy Japanese and Caucasian male subjects.	
	• Sufficient Japanese and Caucasian healthy male volunteer subjects will be enrolled such that 6 subjects of each population complete dosing and critical assessments.	
Analysis Populations	Screened: Consisting of all participants screened in the study.	
	• Screening Failure: Participants who sign the ICF in the study but are never subsequently administered study treatment.	
	Safety: All participants who take at least one dose of study treatment.	
	Pharmacokinetic: This population is defined as all participants administered at least one dose of study treatment and who have PK sample taken and analyzed.	
Hypothesis	• The objectives of this study are to evaluate safety and tolerability of Pyrimethamine and to estimate Pyrimethamine pharmacokinetic parameters in healthy male Japanese and Caucasian subjects. No formal statistical hypotheses will be tested. Descriptive statistics will be used to assess safety and tolerability objectives. An estimation approach will be used to address the pharmacokinetic study objectives, where point estimates and corresponding 95% confidence intervals will be constructed, unless otherwise stated.	

Overview	Key Elements of the RAP
Pharmacokinetic Analyses	• Individual Pyrimethamine plasma concentration-time profiles (by group, and subject) and median/mean (±SD) profiles by group will be plotted and listed.

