4. ANALYSIS POPULATIONS

Population	Definition / Criteria	Analyses Evaluated
Screened	Consisting of all participants screened in the study	Study Population
Screening Failure	Participants who sign the ICF in the study but are never subsequently administered study treatment. All participants who sign the ICF have the screening test in the study.	Study Population
Safety	All participants who take at least one dose of study treatment.	Study PopulationSafety
Pharmacokinetic	This population is defined as all participants administered at least one dose of study treatment and who have PK sample taken and analysed.	• PK

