8.3. Pharmacokinetic Parameters

8.3.1. Derived Pharmacokinetic Parameters

- Derivation of pharmacokinetic parameters will be performed by, or under the direct auspices of, Clinical Pharmacology & Science Promotion Office, GlaxoSmithKline K.K.
- Refer to Appendix 4: Data Display Standards & Handling Conventions (Section 10.4.3 Reporting Process & Standards).
- The pharmacokinetic parameters will be calculated by non-compartmental analysis using Phoenix WinNonlin (version 6.3 or higher)
- All calculations of non-compartmental parameters will be based on actual sampling times recorded during the study.

Pharmacokinetic parameters described in Table 7 will be determined from plasma Pyrimethamine concentration-time data, as data permits.

Table 7 Derived Pharmacokinetic Parameters

Parameter	Parameter Description
AUC(0-24)	Area under the concentration-time curve will be calculated to fixed nominal time 24 hours after administration (AUC(0-24)), using the combination of linear and logarithmic trapezoidal methods (i.e., Linear Up/Log Down calculation method in Phoenix WinNonlin). If a sampling time deviation occurred at nominal time 24 hours after administration (and 24 < t), AUC(0-24) will be calculated using the concentration at time 24 hours after administration post-dose estimated by the method of interpolation. If nominal time 24 hours after administration > t (or if the concentration at time 24 hours after administration was below the limit of quantification), then the concentration (y) at time 24 hours after administration is estimated using λz and last observed Ct according to the formula: $y = Ct(obser) \times e^{-lambda_z z(24-t)}$ Then the following equation will be used to calculate AUC(0-24) where t is the time of last quantifiable plasma concentration. $AUC(0-24) = AUC(0-t) + AUC(t-24)$
AUC(0-t)	If lambda_z is not estimable, AUC(0-24) is not calculated (when 24 > t). Area under the concentration-time curve from time zero time (pre-dose) to the time of last quantifiable concentration (AUC(0-t)) will be calculated by a combination of linear and logarithmic trapezoidal methods. The linear trapezoidal method will be employed for all incremental trapezoids arising from increasing concentrations and the logarithmic trapezoidal method will be used for those arising from decreasing concentrations (i.e., Linear Up/Log Down calculation method in Phoenix WinNonlinl).

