10.1. Appendix 1: Protocol Deviation Management

Details will be referred latest Protocol Deviation Management Plan and data handling will be decided prior to final data base release.

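### The SAP sets no minimum profile length for AUC(0-t), so a withdrawn subject's truncated value is pooled with 504 h profiles in the primary summary

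*SAP*

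**What the plan says.** - **Endpoint.** The SAP synopsis gives the primary endpoint as "Cmax, AUC(0-t), AUC(0-inf), AUC(0-24), tmax, t1/2, CL/F, Vd/F from the plasma concentrations of Pyrimethamine in healthy Japanese male subjects, as data permit".
- **Definition.** SAP 8.3.1 (Table 7) takes AUC(0-t) "from time zero time (pre-dose) to the time of last quantifiable concentration". The end point is thus each subject's own.
- **Population.** The PK population in SAP 4 is "all participants administered at least one dose of study treatment and who have PK sample taken and analysed". Protocol 10.2 is equivalent.
- **Withdrawals.** SAP 10.6.1 states that "all available planned data will be included in summary tables and figures, unless otherwise specified", and also "Withdrawn subjects maybe replaced in the study". Under Protocol 5.2, "additional replacement participants may be recruited and assigned to the same treatment at the discretion of the Sponsor". Protocol 8.3 counts a subject lost to follow-up as withdrawn.
- **Use.** SAP 8.3.2 summarises AUC(0-t) with geometric mean, 95% CI and CVb. Figure 4.9 plots it, with mean and 95% CI, for Japanese beside Caucasian subjects.
- **Exclusions.** SAP 10.4.3 names the parameters that are listed but not summarised, and AUC(0-t) is not among them. SAP 10.5.4 drops parameters reported as NC or ND from summaries and figures. SAP 4.1 mentions deviations that may lead to exclusion, and Appendix 1 adds that "data handling will be decided prior to final data base release".

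**The concern.** Read together, these rules put a subject who leaves early into the AUC(0-t) summary with an area that stops where his sampling stopped. A truncated AUC(0-t) is still calculable, so neither the NC/ND rule nor the as-data-permit proviso takes it out, and the exception allowed for in 10.6.1 is not used for this case.

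The error has a known direction: it lowers the group mean. With six or seven subjects per group, one such value can matter, and if it falls in only one group it can look like an ethnic difference in Figure 4.9. Protocol 5.4 gives the Japanese-Caucasian comparison as a reason for the study. The remaining remedy is a data-handling decision before database release, with no stated criterion, in an open-label study. Removing the subject from the PK population altogether would also discard his valid Cmax, tmax and AUC(0-24).

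**Working it through.** **Inputs.** Half-life 106.9 h and tmax 3.3 h in Japanese subjects (Protocol 3.2); about 90 h in non-Japanese subjects (Protocol 5.4); n=6 per group and CVs of 18.1% (Cmax) and 44.6% (AUC(0-inf)) (Protocol 10.1.1); sampling times from SAP Appendix 2. *Assumptions:* one-compartment oral kinetics, one dropout plus one replacement (n=7), and the AUC(0-inf) CV used for AUC(0-t), for which the documents give none.

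**Step 1: the plan's own precision.** SDlog = sqrt(ln(1 + CV²)), which is 0.1795 for Cmax and 0.4259 for AUC(0-inf). Precision = exp(2.571 × SDlog/√6) − 1 = 20.7% and 56.4%. Both match Protocol 10.1.1.

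**Step 2: share of the area captured.** ke = ln 2/106.9 = 0.00648 per h. Solving ln(ka/ke)/(ka − ke) = 3.3 gives ka = 1.69 per h. With concentration proportional to exp(−ke·t) − exp(−ka·t) at the planned times and linear-up/log-down areas, r = AUC(0-last)/AUC(0-504).

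**Step 3: effect on the summary.** One of seven log values is shifted by ln r:
- geometric mean ratio = r^(1/7)
- expected log variance v = 0.4259² + (ln r)²/7
- CVb = sqrt(exp(v) − 1)
- upper 95% bound relative to the geometric mean = exp(2.447 × sqrt(v/7)) − 1

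Example at 24 h: r = 0.146 and ln r = −1.927. The mean ratio is 0.759. v = 0.1814 + 0.5305 = 0.7119, so CVb = 102% and the upper bound is +118%.

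| Last sample | r | Geometric mean | CVb | Upper bound | Geometric mean, half-life 90 h |
|---|---|---|---|---|---|
| 12 h | 0.073 | −31% | 148% | +171% | −30% |
| 24 h | 0.146 | −24% | 102% | +118% | −23% |
| 48 h | 0.274 | −17% | 72% | +82% | −15% |
| 120 h | 0.560 | −8% | 51% | +56% | −7% |
| 168 h | 0.688 | −5% | 47% | +51% | −4% |
| 336 h | 0.92 | −1% | 45% | +48% | −1% |

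For comparison, six complete profiles give CVb 44.6% and +56.4%.

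**Step 4: sensitivity.** Simulation (half-life 106.9 h) gave a median geometric mean ratio of 0.759 and a median CVb of 99% at 24 h, and 0.949 and 44% at 168 h. If the dropout is not replaced, the ratio is r^(1/6): 0.725 at 24 h and 0.940 at 168 h. If the true AUC(0-t) CV were as low as 18.1%, CVb would rise about 4.4 to 4.8 times at 24 h and 1.2 to 1.3 times at 168 h.

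**The case against.** The strongest reply is that large effects need an unusual dropout. Subjects take one pyrimethamine dose and stay in the unit to Day 8, so samples to 168 h are taken in-house. A subject lost after discharge moves the geometric mean by 4-5%, and the resulting interval (+51% at n=7) is no wider than the +56.4% planned at n=6. This stands. A reader might infer from the 24 h row that the summary would typically lose a quarter and double its CV. The documents do not support that: they give no dropout rate. Nor is a quarter an upper limit, since a 12 h last sample gives about −30%.

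A reader might also infer that anyone leaving before or at Day 8 has a terminal slope fitted over less than one half-life. That is wrong at the later times: 120 h exceeds 106.9 h, and 168/106.9 = 1.57 half-lives. Nor is the pre-release decision the only route out for every parameter. AUC(0-inf), t1/2, CL/F and Vd/F can be reported as NC or ND and then omitted under SAP 10.5.4. What is missing there is a threshold: %AUCex is listed, but no limit is set. That route does not help AUC(0-t).

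It is also true that no hypothesis is tested, AUC(0-t) is one of eight primary parameters, AUC(0-24) has a fixed interval, the group comparison is an exploratory plot, and the listings show Tlast and %AUCex for each subject. A careful reader could spot a short profile. This limits the harm, but the reported mean, CI and plot would still be those the rule produces.

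**Conclusion.** The point holds in a conditional form. Followed as written, the SAP pools a withdrawn subject's truncated AUC(0-t) with 504 h profiles, in the primary summary if he is Japanese and in Figure 4.9 in either group. This biases the geometric mean downward. Under the assumptions listed in the working, the fall is about 1% (last sample 336 h), 5% (168 h), 17% (48 h) or 24% (24 h), and more if earlier. CVb is almost unchanged from 168 h on and about doubles at 24 h. The CVb figures depend on the borrowed CV; the geometric mean ratios do not. With no early dropout there is no effect, and the likelier loss after Day 8 has a small one. I rate this as a cheap improvement, not a flaw that threatens the study.

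**What to change.** In SAP 8.3.2 and 10.6.1, add the following:

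- AUC(0-t) is summarised and plotted only for subjects with quantifiable samples to a pre-set time (e.g. at least 336 h), or whose profile ends in a non-quantifiable terminal sample. Alternatively, compute it over a common interval.
- AUC(0-inf), t1/2, CL/F and Vd/F are reported as ND when %AUCex exceeds a pre-set limit (e.g. 20%).
- Values left out are listed and flagged.
- Cmax, tmax and AUC(0-24) are kept wherever sampling supports them.
- A summary of all subjects is given as sensitivity.

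A strict 504 h requirement would be too severe. A subject who misses only Day 22 shifts the mean by about 1%, and his expected %AUCex is about 11%. Dropping him without replacement leaves n=5 and widens precision to exp(2.776 × 0.4259/√5) − 1, about 70%.

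The cost is some SAP wording, a flag variable and one extra summary; no new data are needed. The downside is that a subject with a short profile leaves the AUC(0-t) summary, which widens the interval somewhat if he is not replaced.

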10.6.2. Handling of Missing Data

Element	Reporting Detail
General	Missing data occurs when any requested data is not provided, leading to blank fields on the collection instrument:
	 These data will be indicated by the use of a "blank" in subject listing displays. Unless all data for a specific visit are missing in which case the data is excluded from the table.
	 Answers such as "Not applicable" and "Not evaluable" are not considered to be missing data and should be displayed as such.

10.6.2.1. Handling of Partial Dates

Element	Reporting Detail
Concomitant Medications	imputed using the following convention:
	 If the partial date is a start date, a '01' will be used for the day and 'Jan' will be used for the month
	 If the partial date is a stop date, a '28/29/30/31' will be used for the day (dependent on the month and year) and 'Dec' will be used for the month.
	The recorded partial date will be displayed in listings.

10.7. Appendix 7: Values of Potential Clinical Importance

10.7.1. Laboratory Values

Haematology				
Laboratory Parameter	Units	Category	Clinical Concern Range	
			Low Flag (< x)	High Flag (>x)
		Male		0.54
Hematocrit	Ratio of 1	Female		0.54
		Δ from BL	↓0.075	
	/1	Male		180
Hemoglobin	g/L	Female		180
		Δ from BL	↓25	
Lymphocytes	x109/ L		8.0	
Neutrophil Count	x109/ L		1.5	
Platelet Count	x109/ L		100	550
While Blood Cell Count (WBC)	x10 ⁹ / L		3	20

Clinical Chemistry				
Laboratory Parameter	Units	Category	Clinical Concern Range	
			Low Flag (< x)	High Flag (>x)
Calcium	mmol/L		2	2.75
Creatinine	μmol/L	Δ from BL		↑ 44.2
Glucose	mmol/L		3	9
Potassium	mmol/L		3	5.5
Sodium	mmol/L		130	150

Liver Function				
Test Analyte	Units	Category	Clinical Concern Range	
ALT/SGPT	U/L	High	≥ 2x ULN	
AST/SGOT	U/L	High	≥ 2x ULN	
AlkPhos	U/L	High	≥ 2x ULN	
T Bilirubin	µmol/L	High	≥ 1.5xULN	
	µmol/L		1.5xULN T. Bilirubin	
T. Bilirubin + ALT		High	+	
	U/L		≥ 2x ULN ALT	

10.7.2. ECG

ECG Parameter	Units	Clinical Concern Range				
		Lower	Upper			
Absolute	Absolute					
Absolute QTc Interval	msec		> 450 [1]			
Absolute PR Interval	msec	< 110 [1]	> 220 [1]			
Absolute QRS Interval	msec	< 75 [1]	> 110 [1]			
Change from Baseline						
Increase from Baseline QTc	msec		> 60 [1]			

NOTES:

10.7.3. Vital Signs

Vital Sign Parameter	Units	Clinical Concern Range	
(Absolute)		Lower	Upper
Systolic Blood Pressure	mmHg	< 85	> 160
Diastolic Blood Pressure	mmHg	< 45	> 100
Heart Rate	bpm	< 40	> 110

^{1.} Represent standard ECG values of PCI for HV studies

10.8. Appendix 8 – Abbreviations & Trade Marks

10.8.1. Abbreviations

Abbreviation	Description
ADaM	Analysis Data Model
AE	Adverse Event
A&R	Analysis and Reporting
AUC	Area under the concentration-time curve
AUC(0-inf)	Area under the concentration-time curve from time 0 to infinity
CDISC	Clinical Data Interchange Standards Consortium
CI	Confidence Interval
Cmax	Maximum observed concentration
CSR	Clinical Study Report
CV_b	Coefficient of Variation (Between)
eCRF	Electronic Case Record Form
ICF	Informed Consent Form
ICH	International Conference on Harmonisation
IDSL	Integrated Data Standards Library
GUI	Guidance
PCI	Potential Clinical Importance
PDMP	Protocol Deviation Management Plan
PK	Pharmacokinetic
QTcF	Frederica's QT Interval Corrected for Heart Rate
QTcB	Bazett's QT Interval Corrected for Heart Rate
RAP	Reporting & Analysis Plan
SAC	Statistical Analysis Complete
SDTM	Study Data Tabulation Model
TFL	Tables, Figures & Listings
GSK	GlaxoSmithKline

10.8.2. Trademarks

Trade	marks of the GlaxoSmithKline Group of Companies	
NONE		

Trademarks not owned by the GlaxoSmithKline Group of Companies
SAS
WinNonlin

10.9. Appendix 9: List of Data Displays

10.9.1. Data Display Numbering

The following numbering will be applied for RAP generated displays:

Section	Tables	Figures	
Study Population	1.1 to 1.7	N/A	
Safety	2.1 to 2.17	N/A	
Pharmacokinetic	3.1 to 3.3	4.1 to 4.13	
Section	Listings		
ICH Listings	1 to 36		
Other Listings	N/A		

10.9.2. Mock Example Shell Referencing

Non IDSL specifications will be referenced as indicated and if required an example mock-up displays provided in Appendix 10: Example Mock Shells for Data Displays.

Section	Figure	Table	Listing
Study Population	POP_Fn	POP_Tn	POP_Ln
Safety	SAFE_Fn	SAFE_Tn	SAFE_Ln
Pharmacokinetic	PK_Fn	PK_Tn	PK_Ln

NOTES:

 Non-Standard displays are indicated in the 'IDSL / TST ID / Example Shell' or 'Programming Notes' column as '[Non-Standard] + Reference.'

10.9.3. Deliverable [Priority]

Delivery [Priority] [1]	Description
SAC [X]	Final Statistical Analysis Complete

NOTES:

1. Indicates priority (i.e. order) in which displays will be generated for the reporting effort.

10.9.4. Study Population Tables

Study F	Study Population Tables					
No.	Population	IDSL / TST ID / Example Shell	Title	Programming Notes	Deliverable [Priority]	
Subject	Disposition					
1.1.	Safety	ES1	Summary of Subject Disposition	Completed or withdrawn and the reason for withdrawal.	SAC [1]	
1.2.	Screened	ES6	Summary of Screening Status and Reasons for Screen Failure	The number (%) of Randomized or screening failure subjects as the screening status, and the reason for screening failure.	SAC [1]	
Protoco	ol Deviation					
1.3.	Safety	DV1	Summary of Important Protocol Deviations	Data is from DV dataset.	SAC [1]	
Popula	tion Analysed					
1.4.	Safety	SP1	Summary of Study Populations		SAC [1]	
Demog	Demographic and Baseline Characteristics					
1.5.	Safety	DM1	Summary of Demographic Characteristics		SAC [1]	
1.6.	Screened	DM11	Summary of Age Ranges	Adults (18-64 years)		
1.7.	Safety	DM5	Summary of Race and Racial Combinations		SAC [1]	

10.9.5. Safety Tables

Safety	: Tables				
No.	Population	IDSL / TST ID / Example Shell	Title	Programming Notes	Deliverable [Priority]
Advers	e Events (AEs)				
2.1.	Safety	AE1	Summary of All Adverse Events by System Organ Class and Preferred Term		SAC [1]
2.2.	Safety	AE5A	Summary of All Adverse Events by Maximum Intensity		SAC [1]
2.3.	Safety	AE1	Summary of All Drug-Related Adverse Events by System Organ Class and Preferred Term		SAC [1]
2.4.	Safety	AE5A	Summary of All Drug-Related Adverse Events by Maximum Intensity		SAC [1]
Labora	tory: Chemistry	y			
2.5.	Safety	LB1	Summary of Chemistry		SAC [1]
2.6.	Safety	LB1	Summary of Chemistry Changes from Baseline		SAC [1]
2.7.	Safety	LB4	Summary of Chemistry Data Shifts from Baseline with Respect to the Normal Range		SAC [1]
Labora	tory: Hematolo	gy			
2.8.	Safety	LB1	Summary of Hematology		SAC [1]
2.9.	Safety	LB1	Summary of Hematology Changes from Baseline		SAC [1]
2.10.	Safety	LB4	Summary of Hematology Data Shifts from Baseline with Respect to the Normal Range		SAC [1]

Safety	Safety : Tables					
No.	Population	IDSL / TST ID / Example Shell	Title	Programming Notes	Deliverable [Priority]	
Labora	tory: Urinalysis	,			-	
2.11.	Safety	UR3b	Summary of Urinalysis (Glucose, Protein, Blood, Ketones, Bilirubin, Urobilinogen nitrite, leukocyte esterase) Data		SAC [1]	
2.12.	Safety	LB1	Summary of Urinalysis (Specific Gravity and pH)		SAC [1]	
ECG						
2.13.	Safety	EG1	Summary of ECG Findings		SAC [1]	
2.14.	Safety	EG2	Summary of ECG Value		SAC [1]	
2.15.	Safety	EG2	Summary of Change from Baseline in ECG Values by Visit		SAC [1]	
Vital Si	Vital Signs					
2.16.	Safety	VS1	Summary of Vital Signs		SAC [1]	
2.17.	Safety	VS1	Summary of Change from Baseline in Vital Signs		SAC [1]	

10.9.6. Pharmacokinetic Tables

Pharma	Pharmacokinetic : Tables					
No.	Population	IDSL / TST ID / Example Shell	Title	Programming Notes	Deliverable [Priority]	
3.1.	PK	PK01: PKCT1	Summary of Pyrimethamine Plasma Concentration		SAC [1]	
3.2.	PK	PK03: PKPT1	Summary of Pyrimethamine Pharmacokinetic Parameters (non-transformed)		SAC [1]	
3.3.	PK	PK05: PKPT3	Summary of Pyrimethamine Pharmacokinetic Parameters (loge-transformed)		SAC [1]	

10.9.7. Pharmacokinetic Figures

Pharmacokinetic: Figures					
IDSL / TST ID / Exam ple Shell	Population	IDSL / TST ID / Example Shell	Title	Programming Notes	Deliverable [Priority]
4.1.	PK	PK16a: PKCF1p	Individual Pyrimethamine Plasma Concentration-Time Plots by Subject (from Pre-Dose to Day 22)	by Subject (Linear and Semi-Log) Time: from Pre-dose to Day 22	SAC [1]
4.2.	PK	PK24: pkcf6	Individual Pyrimethamine Plasma Concentration-Time Plots by group (from Pre Dose to Day 22)	By group (Linear and Semi-Log) Time: from Pre-dose to Day 22	SAC [1]
4.3.	PK	PK19: PKCF4	Mean (+SD) Pyrimethamine Concentration-Time Plots (from Pre Dose to Day 22)	Time: from Pre-dose to Day 22	SAC [1]
4.4.	PK	PK18: PKCF3	Median Pyrimethamine Plasma Concentration-Time Plots (from Pre Dose to Day 22)	Time: from Pre-dose to Day 22	SAC [1]
4.5.	PK	PK16a: PKCF1p	Individual Pyrimethamine Plasma Concentration-Time Plots by Subject (from Pre Dose to 72 hr)	by Subject (Linear and Semi-Log) Time: from Pre-dose to 72 hr	SAC [1]
4.6.	PK	PK24: pkcf6	Individual Pyrimethamine Plasma Concentration-Time Plots by group (from Pre Dose to 72 hr)	By rgroup (Linear and Semi-Log) Time: from Pre-dose to 72 hr	SAC [1]
4.7.	PK	PK19: PKCF4	Mean (+SD) Pyrimethamine Concentration-Time Plots (from Pre Dose to 72 hr)	Time: from Pre-dose to 72 hr	SAC [1]
4.8.	PK	PK18: PKCF3	Median Pyrimethamine Plasma Concentration-Time Plots (from Pre Dose to 72 hr)	Time: from Pre-dose to 72 hr	SAC [1]
4.9.	PK	PK28	Plot of Pyrimethamine Treatment and PK Parameters	AUC(0-t), AUC(0-inf), Cmax, t1/2 Plot and Mean with 95%CI X axis: Japanese, Caucasian Y axis: PK parameters	SAC [1]

Pharma	Pharmacokinetic: Figures					
IDSL / TST ID / Exam ple Shell	Population	IDSL / TST ID / Example Shell	Title	Programming Notes	Deliverable [Priority]	
4.10.	PK	Study Specifics (PK_F1)	Individual Pyrimethamine Plasma Concentration-Time Plots (from Pre-Dose to Day 22)	Japanese & Caucasian (Linear and Semi-Log) Time: from Pre-dose to Day 22	SAC [1]	
4.11.	PK	Study Specifics (PK_F1)	Individual Pyrimethamine Plasma Concentration-Time Plots (from Pre-Dose to 72 hr)	Japanese & Caucasian (Linear and Semi-Log) Time: from Pre-dose to 72 hr	SAC [1]	
4.12.	PK	Study Specifics (PK_F2)	Mean (+SD) Pyrimethamine Concentration-Time Plots (from Pre Dose to Day 22)	Japanese & Caucasian Time: from Pre-dose to Day 22	SAC [1]	
4.13.	PK	Study Specifics (PK_F2)	Mean (+SD) Pyrimethamine Concentration-Time Plots (from Pre Dose to 72 hr)	Japanese & Caucasian Time: from Pre-dose to 72 hr	SAC [1]	

